8. DEMOGRAPHICS AND BASELINE CHARACTERISTICS

Summaries for the demographics and baseline clinical characteristics will be summarized by treatment group for ITT, mITT and the Safety population. Baseline clinical characteristics are defined as the latest data collected on or before date of randomization, if not otherwise specified. When there are retested values, the retest values will be used for the analysis. Individual subject listings will be provided to support the tables.

Summary statistics (mean, standard deviation, median, minimum, and maximum) will be provided for variables measured on a continuous scale. The frequency distribution (n, %) will be provided for those categorical variables measured on a nominal scale.

8.1. Demographics

Demographic characteristics consist of age, gender, race, ethnicity, reproductive status, weight (kg), height (cm), and body mass index (BMI).

Age, collected from Demographic CRF page, will be summarized both descriptively and categorically using the following age categories: (≤ 64 , 65-74, and ≥ 75 years).

Baseline BMI will be summarized both descriptively and categorically using the following categories (<20 , 20- <25 , 25- <30 , ≥ 30 kg/m²) and calculated, using the formula:

$$\text{BMI (kg/m}^2\text{)} = \text{baseline weight (kg)} / (\text{height(m)}^2).$$

Gender, race, ethnicity and reproductive status will be summarized categorically with respect to the categories as specified in the CRF. A by-subject listing of demographic characteristics will be presented.

8.2. Baseline Disease Characteristics

Baseline disease characteristics includes following variables:

- MDS World Health Organization (WHO) 2008 classification,
- Eastern Cooperative Oncology Group (ECOG) performance status (0 – 1, 2),
- Time since initial diagnosis (defined as the number of months from the date of initial diagnosis to the date of randomization),
- IPSS score classification ([Greenberg, 1997, Appendix C](#)),
- Baseline platelet transfusion status (Dependent, Independent),
- Average baseline RBC transfusion requirements (units per 28 days) and category (≤ 4 units per 28 days, > 4 units per 28 days),
- Bone marrow blasts baseline values and category ($< 5\%$, $\geq 5\%$),
- Hgb (g/dL) values,
- Platelet count ($10^9/L$) values,
- Absolute neutrophil count ($10^9/L$) values,
- White blood cell count ($10^9/L$) values,

- Transferrin saturation baseline values (%) values.

Subjects will be considered platelet transfusion dependent at baseline if they have received ≥ 2 platelet transfusions during the 56 days immediately preceding randomization and had no consecutive 28-day period during which no platelet transfusions were administered.

The average number of units (in 28 days) of baseline RBC transfusions is determined by the following rules:

If the subject was randomized under the original protocol and protocol amendment 1, the average number of units per 28 days = sum of RBC transfusion units during the 84-day interval prior to the randomization date / 84 days * 28 days.

- If the subject was randomized under protocol amendment 2, the average number of units per 28 days = sum of RBC transfusion units during the 56-day interval prior to the randomization date / 56 days * 28 days.
- RBC transfusion and whole blood transfusion during the above specified period will be included. For whole blood transfusion, the number of units collected in the CRF will be used to calculate the RBC transfusions required units.

To eliminate the impact of transfusion, the baseline values for Hgb will be determined by following steps:

Step 1: Apply the “7-day rule” on all Hgb values from the Central lab which are collected on or prior to Cycle 1 Day 1. Use the lowest value among the Hgb values which are collected after >7 days of a RBC/whole blood transfusion or collected on the same of the transfusion as the baseline value.

Step 2: For subjects who don’t have baseline value from Step 1, apply the “7/3-day rule”. Use the lowest value among the Hgb values from the Central lab which are collected within 7 days after a RBC/whole blood transfusion and within 3 days before another transfusion as the baseline value. The rationale is that the Hgb value within 7 days from the first transfusion was only somewhat influenced by that transfusion.

Step 3: For subjects who don’t have baseline values from Steps 1 and 2, use the lowest value among all Hgb values from the Central lab which are collected on or prior to Cycle 1 Day 1.

The baseline values for platelet count will be determined similarly to eliminate the impact of platelet transfusion.

For absolute neutrophil count, white blood cell count and bone marrow blasts, the baseline values will be determined by selecting the last non-missing value from the Central lab on or prior to Cycle 1 Day 1. In case that a randomized subject was not treated (no Cycle 1 Day 1 date), the date of randomization will be used.

Baseline transferrin saturation will be derived using the serum samples collected at screening. The transferrin saturation result is derived as: iron (umol/L) / total iron binding capacity (umol/L). In case the result of total iron binding capacity is reported as “<xxx”, xxx-1 will be used as the total iron binding capacity to derive the transferrin saturation.

By-subject listings of the baseline disease characteristics will be provided.

In addition to the above baseline disease characteristics, the revised international prognostic scoring system for MDS (IPSS-R, [Greenberg, 2012, Appendix G](#)) will be summarized for exploratory purpose.

IPSS-R score will be classified and summarized as: very low, low, intermediate, high, very high. The derivation for the IPSS-R score is provided in [Appendix G](#). The revised IPSS cytogenetic classification (from central lab) will also be summarized (very good, good, intermediate, poor, very poor).

[REDACTED]

By-subject listings of IPSS-R will be provided.

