platelet counts in subjects with concomitant thrombocytopenia associated with their MDS. ESAs are less effective for RBC transfusion-dependent anemia than for RBC transfusion-independent anemia (Hellstrom-Lindberg, 2003). Thus the best supportive care for this study should minimize the risk of not providing subjects with appropriate care, while providing the potential benefit of achieving RBC transfusion independence and/or having improvement in platelet counts.

Study Design

This is a phase 3, multicenter, randomized, double-blind, placebo-controlled, parallel-group study. The study consists of 3 phases: Screening, Double-blind treatment, and Follow-up.

Screening Phase

Subject screening procedures are to take place within 56 days prior to randomization.

Independent central review of bone marrow aspirate, biopsy and peripheral blood smear slides, central analysis of cytogenetics, central laboratory hematology result is used to confirm MDS disease and WHO classification (Appendix A) and to determine the IPSS risk classification (Appendix B).

RBC transfusion history must be available for the 56 days immediately preceding and including the date of randomization. Transfusion data should include the type, number of units, reason and date of transfusion. Transfusion data must include the hemoglobin (Hgb) value for which the transfusion was administered. Hemoglobin (Hgb) levels at the time of or within 7 days prior to administration of an RBC transfusion must have been ≤ 10.0 g/dL in order for the transfusion to be counted towards RBC transfusion-dependent status. Red blood cell transfusions administered when Hgb levels were > 10.0 g/dL will not qualify as a required transfusion for the purpose of providing evidence of RBC transfusion-dependent status. In addition, any RBC transfusion administered for elective surgery will not qualify towards determination of RBC transfusion-dependent status at baseline. All RBC transfusion records for 56 days immediately preceding and including the date of randomization should be collected, regardless of Hgb levels.

RBC transfusion-dependent anemia at baseline is defined for this protocol as documentation of an average transfusion requirement of at least 2 units* of RBCs per 28 days during the 56 days immediately preceding and including the date of randomization. There must not be any consecutive 28 days within the 56-day period during which no RBC transfusions were administered.

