The primary efficacy endpoint is the proportion of subjects in the overall population achieving RBC transfusion independence with a duration of ≥ 56 days (8 weeks). Red blood cell transfusions administered during the 56 days immediately preceding and including the date of randomization will be used to establish baseline requirements. Red blood cell transfusions administered during the treatment period will be used in the efficacy analysis. Red blood cell transfusions administered for elective surgery will not be counted towards baseline requirements, efficacy analysis, or progressive disease status.

Secondary efficacy endpoints include OS, HI-P, proportion of subjects in the overall population achieving RBC transfusion independence with duration of ≥ 84 days (12 weeks), duration of RBC transfusion independence, [≥ 84 days (12 weeks) and ≥ 56 days (8 weeks)], time to RBC transfusion independence [≥ 84 days (12 weeks) and ≥ 56 days (8 weeks)], the proportion of subject progressing to AML, time to AML progression, HI-E (IWG 2006 criteria; [Cheson, 2006](#); [Appendix D](#)), duration of RBC transfusion reduction, the proportion of platelet transfusion-dependent subjects at baseline achieving platelet transfusion independence with duration ≥ 56 days (8 weeks), duration of platelet transfusion independence, time to platelet transfusion independence, hematologic response (IWG 2006 criteria; [Cheson, 2006](#); [Appendix D](#)), and the proportion of subjects experiencing clinically significant bleeding events.

Platelet transfusions administered during the 56 days immediately preceding and including the date of randomization will be used to establish baseline requirements. Platelet transfusions administered during the treatment period will be used in the efficacy analysis. Platelet transfusions

administered for elective surgery will not be counted towards baseline requirements, efficacy analysis or progressive disease status.

Overview of Safety Assessments

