Subjects should continue to receive IP for at least 6 cycles of treatment before being assessed for disease status because, based on prior studies with parenteral azacitidine therapy, response to treatment may be significantly delayed ([Silverman, 2006](#)). While on double-blinded treatment, subjects will continue to receive best supportive care, thus the requested 6-month minimum treatment period does not represent an undue risk to subjects. In addition, because overall survival is one of the endpoints, the effect of extended therapy is being evaluated; suspension of therapy at an early time point may blunt any possible extended survival. Crossover between the treatment groups is not allowed so as not to compromise the overall survival endpoint.

The primary endpoint, RBC transfusion independence, is defined as the absence of any RBC transfusion during any consecutive “rolling” 56 days during the treatment period compared with an average transfusion requirement of ≥ 2 units/28 days of RBCs confirmed for a minimum of 56 days immediately preceding and including the date of randomization. Achieving RBC transfusion independence is likely to be a substantial clinical benefit in a patient population with a median overall survival of approximately 14 to 16 months ([Garcia-Manero, 2008a](#); [Cruz, 2010](#); [Yong, 2010](#)).

Analysis of the primary endpoint will be conducted only once after full (100%) information is available for RBC transfusion independence rates (ie, after all subjects have completed 12 months of double-blind treatment or discontinued before reaching 12 months of double-blind treatment). Twelve months was selected as the duration of double-blind treatment based on the same reason mentioned above that a hematologic response to azacitidine treatment may frequently be delayed ([Silverman, 2006](#)).

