7.2 Inclusion Criteria

Subjects must satisfy the following criteria to be enrolled in the study:

1. Age ≥ 18 years[§] at the time of signing the informed consent document
2. Have a documented diagnosis of MDS according to WHO 2008 classification ([Appendix A](#))
3. Be RBC transfusion-dependent as defined by:
 - Average transfusion requirement of ≥ 2 units** per 28 days of RBCs confirmed for a minimum of 56 days immediately preceding randomization (please note that the period covering the transfusion history overlaps with the screening phase)
 - Hemoglobin levels at the time of or within 7 days prior to administration of an RBC transfusion must have been ≤ 10.0 g/dL in order for the transfusion to be counted towards RBC transfusion-dependent status. Red blood cell transfusions administered when Hgb levels were > 10.0 g/dL and/or RBC transfusions administered for elective surgery will not qualify as a required transfusion for the purpose of providing evidence of RBC transfusion-dependent status
 - No consecutive 28 days that are RBC-transfusion-free during the 56 days
 - immediately preceding randomization
4. Have thrombocytopenia as defined by two platelet counts that are $\leq 75 \times 10^9/L$ and ≥ 21 days apart. The second confirmatory platelet count must be obtained ≤ 14 days prior to randomization
 - At least one platelet count must be centrally analyzed within the 56 day screening period with results of $\leq 75 \times 10^9/L$; the second platelet count may be centrally or locally analyzed, with results that are also $\leq 75 \times 10^9/L$.
 - Prior documented medical history of thrombocytopenia may be used to demonstrate eligibility for the study if at least one historical platelet count of $\leq 75 \times 10^9/L$ was obtained within 56 days of randomization and ≥ 21 days apart from the centrally analyzed platelet count.
 - If additional platelet counts were obtained during the interim period, these must also have been $\leq 75 \times 10^9/L$. If platelet counts within the interim period are $> 75 \times 10^9/L$, this would be acceptable only if directly associated with a platelet transfusion administered within 7 days prior to the date of the platelet count.

§ In Japan, both the subject and the subject's legal representative must sign an informed consent document in case the age of the subject has not reached 20 years.

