10.4 Background and Demographic Characteristics

Demographic and baseline disease characteristics will be summarized by treatment group for the ITT, mITT, and safety populations. Subjects' age, height, weight, body mass index (BMI), and continuous baseline characteristics will be summarized using descriptive statistics (N, mean, SDev, median, minimum, maximum), while age group, gender, race and other categorical variables will be provided using frequency tabulations (count, percent) by treatment group. Summaries of baseline disease characteristics will include WHO MDS diagnosis classification, IPSS risk classification, time since initial MDS diagnosis, ECOG performance status, bone marrow blasts (%), Hgb (g/dL), platelet counts ($10^9/L$), average baseline RBC transfusion requirement

(unit of RBC per 28 days), platelet transfusion status (dependent or independent), and IPSS cytogenetic classification. For laboratory and vital sign measures, the most recent assessment on or prior to the date of randomization will be used for baseline. Baseline transfusion history will include all transfusions up to and including the date of randomization.

Medical history data (coded by the Medical Dictionary for Regulatory Affairs [MedDRA] dictionary) will be summarized using frequency tabulations by treatment group, system organ class and preferred term for the ITT, mITT, and safety populations.

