10.1. Analysis of Primary Efficacy Endpoint

The primary efficacy endpoint of RBC transfusion independence is defined as the absence of any RBC transfusion during any consecutive "rolling" 56 days within the treatment period. A subject who did not receive any RBC transfusion during a consecutive rolling 56 days (i.e., day 1 to day 56, day 2 to day 57) will be considered as a 56-day RBC transfusion independent responder. Subjects without achieving the response as defined above, subjects with less than 56 days of assessment during the double-blind treatment period, and subjects who had average baseline RBC transfusion units less than 2 units per 28 days (as defined in Section 8.2) will be counted as non-responders.

All RBC transfusion records on or after randomization within the evaluation period will be used to assess the response for each subject. In other words, the days after the end of the evaluation period will not contribute to a rolling period. The end date of the evaluation period is defined as:

- For a subject who discontinues the treatment,

- If the subject doesn't receive a subsequent MDS treatment, use the date of end of treatment visit;
- If the subject receives a subsequent MDS treatment, use the start date of the subsequent MDS treatment – 1 day, or the date of end of treatment visit, whichever is earlier;
- For a subject who is still on-treatment at the time of the database lock for the primary analysis, the subject's latest available assessment date in the database (from AE, vital sign, local and central lab, study drug records, efficacy assessments) will be used.

The 56-day rolling period for the RBS transfusion independent assessment starts on the date of randomization.

Note if the interval between the last RBC transfusion in the evaluation period (if there is at least one RBC transfusion during the evaluation period) and the end date of the evaluation period is less than 56 days, this rolling period, which is less than 56 days, won't be considered as meeting the transfusion independence criteria even though there is no RBC transfusion in it. The day on which the transfusion is received will not contribute to the 56-day without receiving RBC transfusion rolling period.

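### SAP 8.2 leaves the randomization day out of the baseline RBC window that the protocol includes, so the SAP's 2-unit rule can score a subject who meets the protocol's dependence definition as a non-responder

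*SAP*

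**What the plan says.** **Protocol.** Five places put the randomization date inside the baseline window.

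- The screening text in the Protocol Summary and Section 4.1.1 both define dependence as an average of at least 2 units "of RBCs per 28 days during the 56 days immediately preceding and including the date of randomization".
- The efficacy overview in the Protocol Summary says: "Red blood cell transfusions administered during the 56 days immediately preceding and including the date of randomization will be used to establish baseline requirements".
- Section 4.2 describes the primary endpoint against a requirement of at least 2 units per 28 days, "confirmed for a minimum of 56 days immediately preceding and including the date of randomization".
- Section 10.4 says: "Baseline transfusion history will include all transfusions up to and including the date of randomization".

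Inclusion criterion 3 in Section 7.2 is worded differently. There the requirement is "confirmed for a minimum of 56 days immediately preceding randomization", with no mention of the date itself.

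**SAP.** Section 8.2 derives the average for Amendment 2 subjects as the "sum of RBC transfusion units during the 56-day interval prior to the randomization date / 56 days * 28 days". For subjects under the original protocol or Amendment 1 it is the "sum of RBC transfusion units during the 84-day interval prior to the randomization date / 84 days * 28 days". SAP 4.1.1 asks for transfusion history that includes the randomization date, but then states the dependence definition without that date.

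SAP 10.1 adds "subjects who had average baseline RBC transfusion units less than 2 units per 28 days", by explicit reference to Section 8.2, to the subjects who are automatically non-responders. It also derives the 4-unit stratum for the Mantel-Haenszel test from CRF data by reference to Section 8.2. Protocol 10.6.1 makes only subjects with under 56 days of assessment automatic non-responders. SAP 16 mentions neither the window nor the 2-unit rule, and says that nothing else in the protocol's statistical section has changed.

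**The concern.** The two documents put the randomization day on opposite sides of the baseline boundary. That would matter little if the baseline average were only descriptive. In SAP 10.1, however, it decides whether a subject can be a responder at all. A subject at or just above the dependence threshold who was transfused on the randomization day can satisfy the protocol's definition and then count as a failure in the confirmatory ITT analysis, whatever happens on treatment.

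The day is a plausible one for a transfusion. The first dose may be given on the day of randomization, so it can be a clinic visit for a transfusion-dependent subject.

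**Working it through.** **1. The plan's own power figures.** Inputs from Protocol 10.3: 108 per arm, two-sided alpha 0.05, unpooled variance. Power = Φ(|p1 − p2| / √(p1q1/108 + p2q2/108) − 1.96).

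- 0.15 v 0.05: SE = √((0.1275 + 0.0475)/108) = 0.0403; 0.10/0.0403 = 2.48; power 70.0% (plan: about 70%).
- 0.30 v 0.05: SE = √((0.21 + 0.0475)/108) = 0.0488; 0.25/0.0488 = 5.12; power 99.9% (plan: about 99%).

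Both are reproduced.

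**2. The baseline average under each window.** Average = units / window days × 28. The 2-unit threshold is therefore 4 units in 56 days or 6 units in 84 days. The protocol column counts the randomization day and the SAP column does not. No units are assumed on the extra earliest day of the SAP window.

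| Window | Total units | On randomization day | Protocol average | SAP average | Forced non-responder under SAP |
|---|---|---|---|---|---|
| 56 days | 4 | 1 | 2.0 | 1.5 | yes |
| 56 days | 4 | 2 | 2.0 | 1.0 | yes |
| 56 days | 5 | 1 | 2.5 | 2.0 | no |
| 56 days | 5 | 2 | 2.5 | 1.5 | yes |
| 56 days | 6 | 2 | 3.0 | 2.0 | no |
| 84 days | 6 | 1 | 2.0 | 1.67 | yes |
| 84 days | 6 | 2 | 2.0 | 1.33 | yes |
| 84 days | 7 | 2 | 2.33 | 1.67 | yes |
| 84 days | 8 | 2 | 2.67 | 2.0 | no |

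The current protocol text defines dependence over 56 days only. The 84-day rows rest on the general statement in Section 10.4.

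**3. The stratum.** Nine units in 56 days, 2 of them on the randomization day: 9/56 × 28 = 4.5 (above 4) under the protocol; 7/56 × 28 = 3.5 (at or below 4) under the SAP.

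**4. Effect on power.** The documents give no count, so the fraction f of responders forced to non-response is an assumption, taken as equal in both arms. Each response rate becomes p(1 − f).

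| f | 0.15 v 0.05 becomes | Power | 0.30 v 0.05 becomes | Power |
|---|---|---|---|---|
| 0 | 0.15 v 0.05 | 70.0% | 0.30 v 0.05 | 99.9% |
| 1% | 0.1485 v 0.0495 | 69.5% | 0.297 v 0.0495 | 99.9% |
| 2% | 0.147 v 0.049 | 69.0% | 0.294 v 0.049 | 99.9% |
| 5% | 0.1425 v 0.0475 | 67.5% | 0.285 v 0.0475 | 99.9% |
| 10% | 0.135 v 0.045 | 64.8% | 0.27 v 0.045 | 99.7% |

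**The case against.** **The SAP matches inclusion criterion 3.** The eligibility criterion does not name the randomization date, so the SAP could be said to follow one of the protocol's own wordings. But that criterion is framed by the event of randomization, and units given earlier the same day precede the event. It does not exclude them, and five other places in the protocol include the date. What stands is that criterion 3 should be aligned too.

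**Few subjects can be affected.** Eligibility is verified before randomization, with sponsor review of key criteria. Forced non-response therefore needs a subject near the threshold whose dependence rested on units given that same day. This stands: the group is narrow.

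**The error does not run only one way.** A 56-day window ending the day before randomization gains an earlier day. SAP 8.2 also does not exclude units given at hemoglobin above 10 g/dL or for elective surgery, which do not count toward eligibility. Either can offset a lost unit. This stands as well.

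**The 2-unit rule is not new.** Protocol 4.2 describes the endpoint by comparison with a requirement of at least 2 units per 28 days, so a reader who infers that the rule has no protocol basis goes too far. But the window in that same sentence includes the randomization date. Protocol 10.6.1, the counterpart of SAP 10.1, does not contain the rule.

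Two further inferences are tempting and are not supported:

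- That the Section 8.2 sum also sets the baseline for RBC transfusion reduction. SAP 10.2.11 defines its own 56-day baseline and does not refer to 8.2.
- That starting the rolling period on the randomization date costs subjects a response. SAP 10.1 already keeps a transfusion day out of any transfusion-free run, so a transfusion that day only moves the run to the next day.

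**Conclusion.** The point holds as a real but limited inconsistency. Followed literally, the SAP can make a subject who meets the protocol's dependence definition unable to respond on the primary endpoint. It can also place a subject in a different RBC stratum from the one the protocol's window gives. The rule that carries the mismatch into the endpoint is not declared as a change.

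The number affected is unknown and probably small. On the assumed range of 1% to 10% of responders, the power loss for 0.15 v 0.05 is 0.5 to 5.2 points. For 0.30 v 0.05, power stays at or above 99.7%. A reader might infer bias between arms or an inflated type I error. The documents do not support that: the rule depends on baseline transfusions in a blinded, randomized trial and should affect both arms alike.

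**What to change.** - In SAP 8.2 and 4.1.1, define the baseline window (56 or 84 days) as ending on and including the randomization date. Apply both the 2-unit rule and the 4-unit stratum with that window.
- Add the date to inclusion criterion 3 in Protocol 7.2, so that the protocol agrees with itself.
- List the 2-unit rule in SAP 16 as an addition to Protocol 10.6.1.
- Add a sensitivity analysis of the primary endpoint without the 2-unit rule.

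The start of the rolling period can stay as it is. The cost is a few lines of SAP wording, a one-day change in one derivation and one extra run of the primary analysis. Protocol Amendment 6.0 states that the report of the primary analysis is already final. In practice, then, the sponsor can count the subjects whose responder status or stratum changes under the protocol's window, report that count, and give the primary result with the corrected window and without the rule.
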